#### **Secondary outcomes:**

The difference between UP360, UP446 and placebo at Day 28 and 56 in:

- 1. Number of confirmed COVID-19 infections
- 2. Number of confirmed flu cases
- 3. Impact of COVID-19 on quality of life assessed by the COVID-19 Impact on QoL Questionnaire
- 4. Over-the-counter cold and flu medication use

The difference between UP360, UP446 and placebo at Day 56 in:

- 1. Number of hospitalizations due to COVID-19
- 2. Number of hospitalizations due to flu

The difference in change between UP360, UP446 and placebo from baseline at Day 28 and 56 in:

- 1. Erythrocyte sedimentation rate (ESR) and C-reactive protein (CRP)
- 2. Hematology parameters: white blood cell (WBC) count with differential (neutrophils, lymphocytes, monocytes, eosinophils, basophils), reticulocyte count, red blood cell (RBC) count, hemoglobin, hematocrit, platelet count, RBC indices (mean corpuscular volume (MCV), mean corpuscular hemoglobin (MCH), mean corpuscular hemoglobin concentration (MCHC), and red cell distribution width (RDW)
- 3. Complement C3 and C4 proteins
- 4. Mean global severity index, as measured by area under the curve (AUC) for the Modified Wisconsin Upper Respiratory Symptom Survey (WURSS)-24 daily symptom scores
- 5. Mean symptom severity scores, as measured by AUC for the WURSS-24 daily severity symptom scores
- 6. Number of well days (defined as days scored as 0 (not sick) for the question, "How sick do you feel today?") as assessed by the Modified WURSS-24 Questionnaire
- 7. Number of sick days (defined as days scored as any number from 1 through 7 (sick) for the question, "How sick do you feel today?") as assessed by the Modified WURSS-24 Questionnaire
- 8. Frequency of common upper respiratory tract infection (UTRI) symptoms as assessed by the Modified WURSS-24 Questionnaire
- 9. Duration of common UTRI symptoms as assessed by the Modified WURSS-24 Questionnaire
- 10. Severity of common UTRI symptoms as assessed by the Modified WURSS-24 Questionnaire
- 11. Vitality and quality of life as assessed by the Vitality and Quality of Life (QoL) Questionnaire

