#### Screening assessments include:

- 1. Review medical history, concomitant therapies and current health status
- 2. Assess inclusion and exclusion criteria
- 3. Collect information regarding demographics, alcohol, cannabis, and tobacco habits, diet, sleep, and exercise habits, allergy history, upper respiratory tract infection history, and flu vaccine history
- 4. Collect blood samples for the analysis of CBC, electrolytes (Na, K, Cl), HbA1c, glucose, eGFR, creatinine, AST, ALT, ALP, and total bilirubin
- 5. Dispense modified WURSS-24 Questionnaires and instruct participants on completion. The WURSS-24 Questionnaire is to be completed for the 3 days prior to baseline to establish a preintervention level of upper respiratory tract infection symptoms for each participant and ensure participants are not sick at the time of baseline (Section 9.9.3)
- 6. Dispense study diaries and instruct participants on completion to record the following during the run-in period:
  - a. AEs
  - b. Concomitant medication
  - c. Hours of sleep
  - d. Alcohol intake
  - e. Tobacco use
  - f. Cannabis use
  - g. Hours and description of exercise
  - h. Self-reported COVID-19 diagnosis based on positive COVID-19 test
- 7. Record any pre-emergent AEs

The next appointment will be scheduled within 45 days for potentially eligible participants for their baseline.

Participants will be reminded to follow all instructions provided prior to their next appointment.

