# 11.3 Statistical Analysis Plan

All the primary and secondary endpoints will be analyzed as continuous variables.

For each primary and secondary endpoint, descriptive statistics including number of subjects, arithmetic mean, standard deviation, median, minimum and maximum values will be presented for each study day and for the changes from baseline (Day 0) to each subsequent study day.

Changes in continuous endpoints from baseline will be calculated as:

Change to 
$$V_i = Value$$
 at  $V_i - Value$  at  $V_{baseline}$ 

Differences in changes between groups will be assessed by repeated measures mixed model ANOVA, with study group and visit as the fixed effects. Each model will include the baseline value as a covariate. Within group changes will be assessed by the paired t-test or Wilcoxon Sign Rank test, depending on the distribution of the data. All tests of significance for primary outcomes will be performed at one-sided, and for secondary outcomes will be performed at two-sided, alpha level = 0.05 unless otherwise specified.

The co-primary outcomes will be interpreted individually and together as a real-life global assessment of immune function. As such, there will be no adjustment for multiple outcomes (38-42). This is in accordance with the following principles of the American Statistical Association's statement on statistical significance

and p-values: #3 – "scientific conclusions and business or policy decisions should not be based only on whether a p-value passes a specific threshold;" #4 – "proper inference requires full reporting and transparency;" and #6 – "by itself, a p-value does not provide a good measure of evidence regarding a model or hypothesis" (43).

Missing data for the primary and secondary endpoints will be imputed with last-observation-carried-forward (LOCF) method or multiple imputation as a sensitivity analysis for ITT Population. No imputation will be performed for PP and Safety Population.

Probabilities  $\leq 0.05$  will be considered statistically significant. All statistical analysis will be completed using the R Statistical Software Package Version 3.6.3 or newer for Microsoft Windows (44).

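### Well days and sick days are raw counts listed as change from a 3-day run-in to windows of 24 to 32 days, so the planned change tables and within-group tests largely measure window length

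*Protocol*

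**What the plan says.** The third list of secondary outcomes in Protocol Section 5 opens with "The difference in change between UP360, UP446 and placebo from baseline at Day 28 and 56 in", followed by eleven items. Item 6 is the "Number of well days (defined as days scored as 0 (not sick) for the question" on how sick the participant feels that day. Item 7 is the "Number of sick days (defined as days scored as any number from 1 through 7 (sick) for the question". Both are plain numbers of days with no denominator.

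The same list holds two AUC outcomes (items 4 and 5), of which the second reads "Mean symptom severity scores, as measured by AUC for the WURSS-24 daily severity symptom scores". It also holds "Frequency of common upper respiratory tract infection (UTRI) symptoms as assessed by the Modified WURSS-24 Questionnaire" (item 8) and "Duration of common UTRI symptoms as assessed by the Modified WURSS-24 Questionnaire" (item 9). Neither of these last two has a stated derivation.

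The baseline comes from Section 9.1, where the questionnaire is "to be completed for the 3 days prior to baseline to establish a preintervention level of upper respiratory tract infection symptoms". The same sentence uses it to check that nobody is ill on entry. Section 9.2 fixes the run-in as Day -3 to Day -1. Fresh questionnaires are handed out at Day 0 and Day 28 (Sections 9.4 and 9.6), and the visits at Day 28 and Day 56 each carry a window of ±2 days (Section 1.3).

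Section 11.3 treats every primary and secondary endpoint as continuous and defines change as the visit value minus the baseline value. It adds: "Within group changes will be assessed by the paired t-test or Wilcoxon Sign Rank test, depending on the distribution of the data". No diary outcome is exempted, and nothing in the protocol standardises by days observed.

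**The concern.** A count over 3 days and a count over about 28 days are not on the same scale, and their difference grows with the longer window whatever happens to the participant. Well days and sick days must both tend to rise in every arm, placebo included, even if nobody's health changes.

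At stake are the change-from-baseline summaries and the within-arm p-values. A report that follows the text could show a significant increase in well days on UP360 and on UP446 that says nothing about either product. Unequal individual follow-up adds a second, smaller problem, because raw counts also depend on how many days each participant was observed.

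**Working it through.** The protocol gives no figure for these outcomes, so there is none to reproduce. The sample size in Section 11.1 concerns only the primary outcomes.

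**Inputs**
- Baseline window: 3 days (Sections 9.1 and 9.2).
- Visits: Day 28 ± 2 and Day 56 ± 2 (Section 1.3).
- Participants per arm: 25 randomised; with the stated 20% loss, 25 × 0.80 = 20 (Section 11.1).
- Test level for secondary outcomes: two-sided 0.05 (Section 11.3).
- Daily probability *p* of a sick day: not in the protocol. Assumed 2%, 5%, 10% and 20%, the same before and after baseline.

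**1. Window lengths**
- Day 0 to 28: 28 − 2 = 26 to 28 + 2 = 30 days.
- Day 28 to 56: (56 − 2) − (28 + 2) = 24 to (56 + 2) − (28 − 2) = 32 days.
- Ratio to baseline: 24/3 = 8 to 32/3 = 10.7.
- If the Day 56 value were counted from Day 0, the window would be 54 to 58 days and the mismatch larger.

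**2. A participant who is well every day**

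Change in well days over 28 days: 28 − 3 = +25.

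**3. Unchanged health, window *W***

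Expected change in sick days is (*W* − 3)*p*; in well days it is (*W* − 3)(1 − *p*). The last two columns come from 4,000 simulated trials per setting. *p* varied between persons by a beta distribution with parameters summing to 5, and the paired t-test was applied to raw counts. The Wilcoxon alternative was not simulated.

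| *p* | Sick days, *W* = 28 | Well days, *W* = 28 | Test on sick days rejects (n = 20; n = 25) | Test on well days rejects |
|---|---|---|---|---|
| 2% | 25 × 0.02 = +0.50 | 25 × 0.98 = +24.50 | 13.4%; 25.0% | about 100% |
| 5% | +1.25 | +23.75 | 72.8%; 87.6% | about 100% |
| 10% | +2.50 | +22.50 | 98.8%; 99.8% | about 100% |
| 20% | +5.00 | +20.00 | 100%; 100% | about 100% |

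The nominal rate is 5%.

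**4. AUC**

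A constant daily score of 1 sums to 3 over the run-in and 28 over 28 days, a change of +25. By the trapezoid rule the values are 2 and 27, again +25. Divided by the number of days (or of intervals, for the trapezoid), the change is 0.

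**5. Counts per day observed**

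The expected change is *p* − *p* = 0. Over windows of 24 to 32 days, the paired test on proportions rejects in 4.9–6.3% of runs at *p* = 10–20%. At 2–5% it rejects in 3.8–8.9%, because the counts are small and skewed.

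**6. Comparison between arms**

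With *Y* the follow-up count and *B* the run-in count, the model *Y* − *B* = *a* + *τ*·arm + *β*·*B* + error is the same as *Y* = *a* + *τ*·arm + (*β* + 1)·*B* + error. The arm effect *τ* does not change. A single-visit version was simulated with two arms of 25, *p* = 10%, window lengths of 26 to 30 days in both arms and no true effect. It rejected in 3.7% of 3,000 runs.

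**7. Unequal windows**

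At *p* = 10%, the extreme second windows give 0.10 × 24 = 2.4 against 0.10 × 32 = 3.2 sick days, and 0.90 × 24 = 21.6 against 0.90 × 32 = 28.8 well days. A shorter window lowers both counts.

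**The case against.** The strongest reply is that Section 5 frames every one of these outcomes as a difference between arms. All arms share the same windows, the model carries baseline as a covariate, and step 6 shows that the subtraction then leaves the arm effect alone. That stands. A reader might infer that the treatment comparison itself is biased; the protocol does not support this. Unequal individual windows mainly add noise, and nothing suggests that they differ by arm. The gap of 24 against 32 days is the outer limit, not a typical difference.

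The second reply is that diary derivations belong in a statistical analysis plan, which is not at hand. This holds for items 8 and 9: a rate, or a duration per episode, would not scale with the window in this way. It holds in part for items 4 and 5, whose titles contain the word *mean* and may intend division by days. It does not hold for items 6 and 7. There the protocol has itself fixed a raw count, a change formula and a within-group test.

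The third reply is that sick days may be rare in healthy adults checked on entry. This also stands. A reader might infer that every arm must show a highly significant rise in both counts, but that is near-certain only for well days. For sick days it depends on a rate that the protocol does not give.

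Finally, a reader might infer that early leavers will look healthier. On sick days they would; on well days the same person looks less healthy.

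**Conclusion.** The point holds for well days and sick days. As written, the change-from-baseline tables and within-group tests for items 6 and 7 mix health with an 8- to 10.7-fold difference in window length. For well days the artefact is about +25 days in a fully well participant, and the test rejects almost always. For sick days the false rejection rate is above 5% at every rate examined, from 13–25% at an assumed 2% to about 99% at 10%. These rates rest on the assumed *p*, the assumed spread between persons and 20 to 25 participants per arm.

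The point extends to AUC (items 4 and 5) unless it is divided by days, and to frequency and duration (items 8 and 9) only if they are window totals. It does not reach severity (item 10) if that is an average score, since an average does not grow with the window.

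Raw counts are also distorted where follow-up is cut short by withdrawal or by removal for illness: COVID-19 or flu before vaccination (Section 9.5), or COVID-19 afterwards (Section 9.7). Those who fall ill may then contribute fewer diary days.

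These are secondary outcomes and the randomised comparison survives the subtraction, so this should be corrected but does not threaten the trial's main analysis.

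**What to change.** In Sections 5 and 11.3:

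- Define items 6 and 7 for each period (Day 0 to 28 and Day 28 to 56) as the proportion of completed diary days scored well or sick. Alternatively, use a binomial model with diary days as denominator or a count model with diary days as offset; the sentence that treats all endpoints as continuous then needs an exception. On completed days the two proportions sum to one, so one analysis serves both.
- Divide AUC in items 4 and 5 by days observed, and say so.
- State how items 8 and 9 are derived. If they are window totals, put them on a per-day scale too.
- Drop the raw-count change from baseline and its within-group tests.
- Use the run-in mean daily score or proportion only as a covariate.
- Leave item 10 as it is if it is an average score.

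The cost is wording only. The daily questionnaires already supply the number of completed days, so no new data or visits are needed.

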### **Outcomes for future analysis:**

The difference in change between UP360, UP446 and placebo from baseline at Day 28 and 56 in:

- 1. Cytokines (GM-CSF; IFN- $\alpha$ ; IFN- $\gamma$ ; IL-1 $\alpha$ ; IL-1 $\beta$ ; IL-1RA; IL-2; IL-4; IL-5; IL-6; IL-7; IL-9; IL-10; IL-12 p70; IL-13; IL-15; IL17A; IL-18; IL-21; IL-22; IL-23; IL-27; IL-31; TNF- $\alpha$ ; TNF- $\beta$ /LTA 150)
- 2. High mobility group box 1 (HMGB1) protein, nuclear factor kappa B (NF-κB), nuclear factor erythroid 2-related factor 2 (Nrf-2)
- 3. Oxidative stress as assessed by 8-iso-prostaglandin F2α, catalase (CAT), glutathione peroxidase (GSH-Px), superoxide dismutase (SOD), malondialdehyde (MDA) and advanced glycation endproducts (AGEs)
- 4. Hemagglutinin inhibition (HI) titers for specific strains of virus

# **Safety outcomes:**

- 1. Clinical chemistry parameters: alanine aminotransferase (ALT), aspartate aminotransferase (AST), alkaline phosphatase (ALP), total bilirubin, creatinine, electrolytes (Na+, K+, Cl-), estimated glomerular filtration rate (eGFR), glucose
- 2. Incidence of pre-emergent and post-emergent adverse events
- 3. Vital signs (blood pressure (BP) and heart rate (HR))

#### 6 STUDY DESIGN

Figure 1: Study Design

[figure not shown]
[figure not shown]

Figure 2: Timeline from screening to end-of-study period

The planned sample size for this study is 75. In order to evaluate study outcomes, study assessments will be conducted as per the Schedule of Assessments in Section 1.3.

Study Arm	Number of Participants
UP360 + Flu Vaccine	N = 25
UP446 + Flu Vaccine	N = 25
Placebo + Flu Vaccine	N = 25
Total	N = 75

#### 7 SELECTION OF STUDY POPULATION

This study will enroll 75 healthy participants. One gender will not exceed 65%. Each participant must fulfill the inclusion criteria and not meet any of the exclusion criteria as described in Sections 7.1 and 7.2, respectively.

## 7.1 Inclusion Criteria

- 1. Males and females between 40 and 80 years of age, inclusive
- 2. Female participant is not of child-bearing potential, defined as females who have undergone a sterilization procedure (e.g. hysterectomy, bilateral oophorectomy, bilateral tubal ligation, complete endometrial ablation) or have been post-menopausal for at least 1 year prior to screening

Or.

Females of child-bearing potential must have a negative baseline urine pregnancy test and agree to use a medically approved method of birth control for the duration of the study. All hormonal birth control must have been in use for a minimum of three months. Acceptable methods of birth control include:

- Hormonal contraceptives including oral contraceptives, hormone birth control patch (Ortho Evra), vaginal contraceptive ring (NuvaRing), injectable contraceptives (Depo-Provera, Lunelle), or hormone implant (Norplant System)
- Double-barrier method
- Intrauterine devices
- Non-heterosexual lifestyle or agrees to use contraception if planning on changing to heterosexual partner(s)
- Vasectomy of partner at least 6 months prior to screening
- 3. Participants who have not yet but are willing to receive the influenza vaccine
- 4. Agrees to provide a verbal history of flu vaccination
- 5. Agrees to maintain current lifestyle habits as much as possible throughout the study depending on your ability to maintain the following: diet, medications, supplements, exercise, and sleep and avoid taking new supplements
- 6. Healthy as determined by medical history and laboratory results as assessed by Qualified Investigator (OI)
- 7. Willingness to complete questionnaires and diaries associated with the study and to complete all clinic visits
- 8. Provided voluntary, written, informed consent to participate in the study

# 7.2 Exclusion Criteria

- 1. Women who are pregnant, breast feeding, or planning to become pregnant during the study
- 2. Participant has a known allergy to the active or inactive ingredients in UP360, UP446, placebo, or QIV
- 3. Unvaccinated participants with flu prior to baseline from September 2020 or prior to Day 28 vaccination
- 4. Participants self-reporting a diagnosis of COVID-19 prior to baseline or prior to Day 28 vaccination
- 5. Participants who have received the COVID-19 vaccine
- 6. Current use of prescribed immunomodulators (including corticosteroids) such as immunosuppressants or immunostimulants within 4 weeks of baseline (see Section 7.3)
- 7. Current use of dietary supplement or herbal medicines associated with boosting or modulating the immune system unless willing to washout (see Section 7.3.2)

- 8. Participation in other clinical research studies 30 days prior to enrollment will be assessed on a caseby-case basis by the QI
- 9. Individuals who are unable to give informed consent
- 10. Any other condition, chronic disease, or lifestyle factor, that, in the opinion of the QI, may adversely affect the participant's ability to complete the study or its measures or pose significant risk to the participant

#### 7.3 Concomitant Medications, Over-the-counter Medications, Supplements and Food/Drinks

Participants who are taking any prescribed medications, over-the-counter (OTC) medications, supplements, or food/drinks that are considered not to affect the study outcomes and are on stable dosage must agree to maintain their current dosing regimen during the study unless otherwise recommended by their general practitioner/nurse practitioner. Participants on medications will be assessed on a case-by-case basis to ensure their eligibility and safety with special reference to the medications listed in the Investigator's Brochure.

#### 7.3.1 Prescribed Medications

Participants on the following concurrent prescribed medications and/or treatments will be excluded during enrollment unless they have been taken off these therapies by their family physician. In the latter event, the frequency of use and/or dosage may be considered by the QI on a case-by-case basis prior to recommending an appropriate washout or their enrollment in the study.

- 1. HMG-CoA reductase inhibitors (statins)
- 2. Immunomodulators (including corticosteroids) such as immunosuppressants or immunostimulants
- 3. Thiazides and other potassium-wasting diuretics assessed by QI on a case-by-case basis

# **7.3.2** Dietary Supplements

Participants who are currently consuming the following supplements will not be allowed to participate unless willing to undergo the specified washout period prior to their baseline visit and agree not to take the supplements during the study. Other OTC supplements and food/drinks will require a case-by-case assessment by the QI based on dose and/or frequency of use to determine adequate washout. All washouts to be ensured to happen prior to enrollment.

- 1. Senegalia catechu (2-day washout)
- 2. Scutellaria baicalensis (7-day washout)
- 3. Aloe vera
- 4. Rosemary extract
- 5. Echinacea (2-day washout)
- 6. Astragalus (2-day washout)
- 7. Ginseng (25-day washout)
- 8. Turmeric (3-day washout)
- 9. Medicinal mushroom
- 10. Probiotics (30-day washout)
- 11. Beta-glucan (30-day washout)

#### 7.4 Washout Periods

Please refer to Section 7.3.2 for washout periods for dietary supplements.

#### 7.5 Early Withdrawal

#### Personal reasons

As stated in the Informed Consent Form, a participant may withdraw from the study for any reason at any time.

## Removal by Qualified Investigator

Participant discontinuation should be considered at the discretion of the Qualified Investigator. The circumstances of any discontinuation must be documented in detail in the participant file and final report. If possible, the evaluations planned for the end of study will be carried out at the time when the participant is withdrawn from the study.

Criteria for removal of participants from the study includes:

#### Clinical reasons

A participant may be withdrawn from the study if, in the opinion of the Qualified Investigator, it is not in the participant's best interest to continue. Any participant who experiences a serious adverse event (SAE) may be withdrawn from the study at the discretion of the Qualified Investigator. A participant will also be withdrawn due to adverse events causing clinically significant illness or the need for prohibited medication(s) during the study. Any female participant who becomes pregnant during the study will be withdrawn and followed up with until giving birth.

## Protocol violation

Any participant found to have entered this study in violation of the protocol will be discontinued from the study at the discretion of the Qualified Investigator. This will include any participant found to have been inappropriately enrolled (did not meet eligibility criteria). Participant non-compliance includes failure to show up for study visits, failure to take the investigational product as directed, or refusal to undergo study visit procedures. Participants who are found to be taking prohibited medications or supplements without the knowledge of the Qualified Investigator will also be withdrawn. Any major protocol deviations (i.e. those that increase the risk to participants and/or compromise the integrity of the study or its results) will result in participant discontinuation.

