#### Assessments include:

- 1. Return and review study diaries and modified WURSS-24 Questionnaires
- 2. Return unused investigational product in the original packaging and remnants and calculate compliance by counting the returned unused investigational product
- 3. Review concomitant therapies and adverse events
- 4. Seated BP and HR measurements
- 5. Collection of blood samples for the analysis of:
  - a. CBC, electrolytes (Na, K, Cl), glucose, eGFR, creatinine, AST, ALT, ALP, and total bilirubin
  - b. ESR, CRP, complement C3, complement C4, IgG, IgM, IgA, CD3+, CD8+, CD4+, CD45+, TCR $\gamma\delta$ +, CD3-CD16+CD56+
  - c. Cytokines, HMGB1, NF-κB, Nrf-2, 8-iso-prostaglandin F2α, CAT, GSH-Px, SOD, MDA, AGEs, HI titers for specific strains of virus for future analysis
- 6. Administer Vitality Questionnaire (Section 9.9.4)
- 7. Administer COVID-19 QoL (Section 9.9.5)
- 8. Administer flu vaccine (QIV)
- 9. Dispense new IP
- 10. Dispense new study diaries
- 11. Dispense new modified WURSS-24 Questionnaires (Section 9.9.3)

The next appointment will be scheduled for Day  $56 \pm 2$  days.

Participants will be reminded to follow all instructions provided prior to their next appointment.

## 9.7 Processing Participants who get COVID-19 or Flu After Vaccination and Prior to Day 56

The WURSS-24 Questionnaires and daily diaries will be reviewed by clinic staff. Clinic staff will identify those participants that self-report they have COVID-19 or flu. Regarding flu, participants will be queried on if they have a diagnosis from their PCP. In the absence of such a diagnosis, based on indicated symptoms, participants will be assessed on a case-by-case basis by the QI.

Participants with self-reported diagnosis COVID-19 will be removed from the study. A COVID-19 diagnosis will be considered an AE and AE follow-up procedures will be followed.

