#### Assessments include:

1. Return and review study diaries and modified WURSS-24 Questionnaires

- 2. Return unused investigational product in the original packaging and remnants and calculate compliance by counting the returned unused investigational product
- 3. Review concomitant therapies and adverse events
- 4. Urine pregnancy test for female potential participants that are of child-bearing potential
- 5. Seated resting BP and HR measurements
- 6. Weight measurement
- 7. Collection of blood samples for the analysis of:
  - a. CBC, electrolytes (Na, K, Cl), glucose, eGFR, creatinine, AST, ALT, ALP, and total bilirubin
  - b. ESR, CRP, complement C3, complement C4, IgG, IgM, IgA, CD3+, CD8+, CD4+, CD45+, TCR $\gamma\delta$ +, CD3-CD16+CD56+
  - c. Cytokines, HMGB1, NF-κB, Nrf-2, 8-iso-prostaglandin F2α, CAT, GSH-Px, SOD, MDA, AGEs, HI titers for specific strains of virus for future analysis
- 8. Administer Vitality Questionnaire (Section 9.9.4)
- 9. Administer COVID-19 QoL (Section 9.9.5)

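### Section 7.5 ends study follow-up, not just product, for two prohibited-product grounds; a participant removed at or before Day 28 then has no post-vaccination sample

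*Protocol*

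**What the plan says.** Section 7.5 (Removal by Qualified Investigator) first places discontinuation at the discretion of the Qualified Investigator. It then introduces the grounds with "Criteria for removal of participants from the study includes". Three statements under that heading matter here:

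- Clinical reasons: withdrawal is stated as certain when it is "due to adverse events causing clinically significant illness or the need for prohibited medication(s) during the study". Serious adverse events and best-interest withdrawal, in the same paragraph, are worded as optional.
- Protocol violation: "Participants who are found to be taking prohibited medications or supplements without the knowledge of the Qualified Investigator will also be withdrawn". Inappropriate enrolment, in the same paragraph, is left to the investigator's discretion.
- Protocol violation, last sentence: major deviations, including those that "compromise the integrity of the study or its results) will result in participant discontinuation".

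The only data provision on removal is: "If possible, the evaluations planned for the end of study will be carried out at the time when the participant is withdrawn". The Participant Replacement paragraph asks that unnecessary withdrawal be avoided, but does not mention these grounds. Section 10.2.2 takes participants off product while keeping them at all remaining visits, but only after participant-initiated withdrawal or clinically significant unexplained laboratory values.

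Section 5 sets the primary outcome as change from baseline at Day 28 and Day 56. In section 9.6 the Day 28 visit lists, in order, "Return and review study diaries and modified WURSS-24 Questionnaires" (item 1), "Review concomitant therapies and adverse events" (item 3), the blood draw (item 5) and the vaccine (item 8). The next scheduled draw is Day 56 (sections 1.3, 9.8 and 9.10).

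**The concern.** Taking a prohibited product is an event after randomization. The usual course is to record it, stop study product if needed, and keep measuring; whether the values count can be decided at analysis. Section 7.5 instead stops the measuring. The ITT population in section 11.2 could use later data from these participants, but the withdrawal rule prevents their collection, and no analysis plan can restore them.

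The trial is built on a vaccine challenge, and Day 56 is the only visit that observes the response to it. Removal for an adverse-event need for a prohibited medicine may be related to treatment, so the resulting gaps need not be random.

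**Working it through.** **What each time of removal costs.** Inputs: 56 days on product, vaccine on Day 28, post-baseline draws at Day 28 and Day 56, windows of ±2 days (sections 1.3, 8.6 and 9.6 to 9.8). Share of diary days lost = (56 − day of removal) / 56. Timing of the exit evaluation = day of removal − 28, against +28 for the planned Day 56 draw.

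| Removed on | Diary days lost | Exit evaluation relative to vaccination |
|---|---|---|
| Day 14 | 42/56 = 75% | 14 days before |
| Day 28 | 28/56 = 50% | same visit; repeats the Day 28 panel |
| Day 42 | 14/56 = 25% | 14 days after, instead of 28 |
| Day 56, visit completed | 0 | the planned draw itself |

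With the windows, the Day 28 to Day 56 gap runs from 54 − 30 = 24 to 58 − 26 = 32 days. Removal at Day 28 loses 1 of 2 scheduled post-baseline draws and 1 of 1 post-vaccination draws. Because the reviews are listed before the vaccine, that participant may also leave unvaccinated.

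Undisclosed use would normally surface at the diary and therapy reviews, which after baseline fall only on Day 28 and Day 56. Removal between visits (the Day 14 and Day 42 rows) therefore applies mainly to the adverse-event ground.

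**Against the sample size.** Section 11.1 plans 25 per arm with 20% loss: 25 × 0.20 = 5 losses, leaving 20, and 20 / (1 − 0.20) = 25, so that step reproduces. One removal is 1/25 = 4% of an arm and one of the 5 allowed losses. The stated detectable differences cannot be reproduced because no standard deviations are given.

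**Illustration of size (assumed inputs).** Suppose k participants in one arm lack a Day 56 value and differ from the rest by d SD. The arm mean is then off by k × d / 25:

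- k = 1: d = 0.5 gives 0.02 SD; d = 1 gives 0.04 SD.
- k = 3: d = 0.5 gives 0.06 SD; d = 1 gives 0.12 SD.

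With 20 v 20 and 80% power, a t-test detects 0.909 SD (two-sided 5%) or 0.801 SD (one-sided 5%). The range is thus 0.02 / 0.909 = 2% to 0.12 / 0.801 = 15% of the detectable difference.

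If removals came on top of the 20% allowance, in both arms of a pairwise one-sided comparison, power (normal approximation) would fall from 80.0% at 20 per arm to 78.2% at 19, 76.2% at 18 and 74.1% at 17.

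**The case against.** **Discretion.** The section opens with investigator discretion and elsewhere warns against unnecessary withdrawal. This stands in part. A reader might infer that 7.5 leaves no room for judgement at all; the text does not support that. It does show a general discretion clause beside firm wording for two specific grounds, in paragraphs that use permissive wording for other grounds. An investigator following the specific sentences would remove the participant.

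**Narrow trigger.** The Protocol violation sentence covers only use without the investigator's knowledge, and a participant who records a product in the diary has arguably disclosed it. Ordinary cold and flu medicines are on neither list in 7.3. Both points reduce the likely number of cases; neither changes what happens to a case.

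**Small effect.** A participant removed after the Day 28 draw keeps the baseline and Day 28 values and stays in the ITT population. The mixed model in section 11.3 uses them, and the arm-mean formula above gives no credit for that. The 20% allowance may absorb some removals. A reader might take the 15% figure as an expected bias, but it needs three removals in one arm, all differing by a full SD in the same direction, with no offset in the comparator. A reader might also infer that LOCF puts pre-vaccination values into the main Day 56 result. The LOCF sentence can be read as covering sensitivity analyses only, so that is not established.

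**Contamination.** Four barred supplements (Senegalia catechu, Scutellaria baicalensis, aloe vera, rosemary extract) are ingredients of the test products, so a placebo participant taking one is contaminated for biomarker outcomes. That is a reason to leave such values out of some analyses. It is not a reason to leave them uncollected.

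**Other grounds.** Adverse events causing clinically significant illness, and COVID-19 after vaccination (section 9.7), also lead to removal and can cost the Day 56 draw. That is true. The point here is confined to the prohibited-product grounds and to the last sentence of Protocol violation.

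**Conclusion.** The point holds as a cheap improvement in data retention. For an adverse-event need for a prohibited medicine and for undisclosed use of a prohibited product, section 7.5 ends participation in the study, and section 10.2.2 offers no alternative. Removal at or before Day 28 leaves no post-vaccination value, and the exit evaluation cannot replace it because it falls before or at vaccination. Use found at Day 56 costs nothing if the visit is completed.

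The total effect cannot be determined, because no rate of prohibited use is given. It is probably small, and its direction is unknown. The 2% to 15% range and the power figures rest on assumed numbers of removals, and the range also on assumed differences; they indicate scale only.

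A reader might go further and conclude that any use of a barred product should exclude a participant from the Per Protocol population. Section 11.2 does not support that: it excludes only deviations that affect primary outcomes, and nothing in the document shows that test to be inadequate.

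**What to change.** In section 7.5, under Clinical reasons and Protocol violation, state for these two grounds:

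- Record the product, dates and reason.
- Stop investigational product if the Qualified Investigator judges it necessary.
- As in section 10.2.2, continue the Day 28 vaccination (unless medically inadvisable), diaries, WURSS-24, visits and blood draws to Day 56 for the ITT analysis, unless the participant declines or safety requires withdrawal.

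Amend the last sentence of Protocol violation so that deviations of this kind lead to discontinuation of product, not of follow-up; otherwise it would bring the removal back. Leave Per Protocol membership to the existing test in section 11.2.

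The cost is wording in two paragraphs. All visits and draws are already scheduled. The downside is that the ITT population will hold a few values taken under other immune-active products; the Per Protocol analysis or a sensitivity analysis can exclude them.
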